7.2 Continuation on Study Treatment After Radiologic Disease Progression

This section details the conditions necessary to allow continued treatment with tarlatamab after radiologic disease progression in subjects that continue to have clinical benefits in the investigator's judgement, provided all of the following criteria are met at each occurrence:

- Absence of threat to vital organs or critical anatomical sites (eg, respiratory failure due to tumor compression, spinal cord compression) requiring urgent alternative medical intervention with persistent immediate threat to vital organs after intervention. The presence of brain metastases may be allowed, provided the lesions are amenable to radiation therapy or dexamethasone (or corticosteroid equivalent) and the subject is clinically stable as per investigator's judgment.
- No other treatment discontinuation criteria are met.
- No significant, unacceptable, or irreversible toxicities related to any dose of the study treatment or treatment related adverse events of CTCAE grade 4 at the current dose at the time of progression.
- The subject is willing to undergo biopsy of one of the new or progressing lesions. If tumor biopsy is not clinically feasible or advisable, the subject may continue only upon agreement with the investigator and the Amgen Medical Monitor.
- Approval for continuation from the Amgen Medical Monitor.
- Palliative radiation for new, progressive, or symptomatic lesions is permitted as per Section 6.1.7. Tarlatamab must be held during treatment and radiation and must be completed at least days before the subsequent dose of tarlatamab.
- All protocol-mandated procedures must be performed as noted in the Schedule of Activities (Section 1.3) (imaging, labs, and clinic visits may be obtained earlier per clinical judgment and if clinically indicated).

7.3 Subject Discontinuation/Withdrawal from the Study

Withdrawal of consent for a study means that the subject does not wish to receive further protocol-required therapies or procedures, and the subject does not wish to or is unable to continue further study participation. Subject data up to withdrawal of consent will be included in the analysis of the study, and where permitted, publicly available data can be included after withdrawal of consent. The investigator is to discuss with the

Protocol Number: 20200439

Date: 05 June 2024 Page 90 of 176

subject appropriate procedures for withdrawal from the study and must document the subject's decision to withdraw in the subject's medical records.

If a subject withdraws from the study, he/she may request destruction of any samples taken and not tested, and the investigator must notify Amgen accordingly (see Section 11.6 for further details). Refer to the Schedule of Activities (Section 1.3) for data to be collected at the time of study discontinuation and follow-up and for any further evaluations that need to be completed.

7.3.1 Reasons for Removal from Study

Reasons for removal of a subject from the study are:

- Decision by sponsor
- Withdrawal of consent from study
- Death
- Lost to follow-up

7.4 Lost to Follow-up

A subject will be considered lost to follow-up if they repeatedly fail to return for scheduled visits and is unable to be contacted by the study site.

The following actions must be taken if a subject fails to return to the clinic for a required study visit:

- The site must attempt to contact the subject and reschedule the missed visit as soon
 as possible and counsel the subject on the importance of maintaining the assigned
 visit schedule and ascertain whether or not the subject wishes to and/or is able to
 continue in the study.
- In cases in which the subject is deemed lost to follow-up, the investigator or
 designee must make every effort to regain contact with the subject (where possible,
 3 telephone calls and, if necessary, a certified letter to the subject's last known
 mailing address or local equivalent methods). These contact attempts are to be
 documented in the subject's medical record.
- If the subject continues to be unreachable, he/she will be considered to have withdrawn from the study with a primary reason of lost to follow-up.
- For subjects who are lost to follow-up, the investigator should search publicly available records where permitted to ascertain survival status. This ensures that the data set(s) produced as an outcome of the study is/are as comprehensive as possible.

8. Study Assessments and Procedures

Study procedures and their time points are summarized in the Schedule of Activities (see Section 1.3).

Protocol Number: 20200439

Date: 05 June 2024 Page 91 of 176

If an enrolled subject is subsequently determined to be ineligible for the study, this must be discussed with the sponsor immediately upon occurrence or awareness to determine if the subject is to continue or discontinue study treatment.

Adherence to the study design requirements, including those specified in the Schedule of Activities, is essential and required for study conduct.

8.1 General Study Periods

8.1.1 Screening, Enrollment and/or Randomization

Informed consent must be obtained before completing any screening procedure or discontinuation of standard therapy for any disallowed therapy. After the subject has signed the ICF, the site will register the subject manually and screen the subject in order to assess eligibility for participation. The screening window is up to

All screening evaluations must be completed and reviewed to confirm that potential subjects meet all eligibility criteria. The investigator will maintain a screening log to record details of all subjects screened and to confirm eligibility or record reasons for screening failure, (see Section 5.4) as applicable.

If a subject has not met all eligibility criteria at the end of the screening period, the subject will be registered as a screen fail. Screen fail subjects may be eligible for re-screening 1 time.

Rescreen subjects must first be registered as screen failures and subsequently registered as rescreens. Once the subject is registered as rescreened, a new screening window will begin. Subjects will retain the same subject identification number assigned at the original screening. If the rescreening period begins more than 30 days after the original signing of the ICF, all screening procedures, including informed consent, must be repeated.

8.1.3 Safety Follow-up

The procedures to be completed during SFU are indicated in the Schedule of Activities (Section 1.3). Upon permanent discontinuation from the study treatment for any reason, an SFU visit will be performed approximately after the last dose (tarlatamab or AMG 404) or prior to initiation of other therapy, whichever occurs first. The second safety follow-up visit will be performed approximately after the end of the last dose of AMG 404 or prior to initiation of other therapy, whichever occurs first.

Protocol Number: 20200439

Date: 05 June 2024 Page 93 of 176

Subjects who discontinue AMG 404 but remain on treatment with AMG 757 will continue to have safety event collection at regularly scheduled study visits. The second safety follow-up visit need only occur if has not elapsed from the end of AMG 404 treatment at the time of end of study treatment.

8.1.4 Long-term Follow-up

Long term follow-up will be conducted every 3 months (\pm 2 weeks) up to 1 year from the first dose of tarlatamab for all subjects who have not withdrawn consent by clinic visit, telephone, or chart review to assess for survival and/or the commencement of subsequent cancer therapy only.

For subjects who discontinued treatment for any reason other than confirmed progressive disease, every effort should be made to perform radiographic imaging (computed tomography [CT]/MRI) of the chest, abdomen, pelvis, and all other known sites of disease every 3 months until documentation of confirmed disease progression per modified RECIST 1.1, clinical progression, start of new anticancer therapy, or up to 12 months after the first dose of tarlatamab, whichever occurs first.

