1.2 Study Schema

C = cvcle: DLT = dose level toxicity; FIH = first-in-human; IV = intravenous; PD = pharmacodynamics; Ph1 = phase 1; PK = pharmacokinetics;

^a The starting dose and associated dosing schedule of tarlatamab will be a target dose of mg with 1-step dosing

b If the combination is not tolerated (based on target DLT rate > 30%), AMG 404 may be administered on cycle 1 Based upon emerging PK, PD, and safety data in the current study as well as the ongoing FIH study (20160323), alternative (intermediate) dose cohort levels,

as part of the de-escalation recommendations may be explored (see Section 4.1 and Figure 4-1 for study

design details pertaining to footnote b)

Study Periods:

- Screening: up to before enrollment
- Treatment: treatment continues until confirmed radiographic progression or disease progression*
- End of treatment: should occur as soon as possible (within a after the last dose of investigational product
- Safety follow-up: approximately after the end of the last dose of tarlatamab and approximately days after the last dose of AMG 404
- Long-term follow-up: every 3 months (± 2 weeks) up to 1 year from the first dose of tarlatamab for all subjects who have not withdrawn consent by clinic visit, telephone, or chart review to assess for survival and/or the commencement of subsequent cancer therapy only

Protocol Number: 20200439

Date: 05 June 2024 Page 18 of 176

*Note: Subjects with confirmed disease progression per modified RECIST 1.1 criteria who have clinical benefit in the investigator's judgment may be allowed to continue treatment after approval by the Medical Monitor as per Section 7.2.

Protocol Number: 20200439

Date: 05 June 2024 Page 19 of 176

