4.1 Overall Design

This is a phase 1b, multicenter, open-label study evaluating the safety, tolerability, PK, pharmacodynamics (PD), and efficacy of tarlatamab in combination with AMG 404 in subjects with SCLC. The study will consist of dose exploration (Part 1) and dose

Protocol Number: 20200439

Date: 05 June 2024 Page 41 of 176

expansion (Part 2). Study enrollment ended in January 2023. A total of subjects were enrolled including subjects in Part 1, and subjects in Part 2.

Part 1 (Dose Exploration):

The dose exploration part of the study will estimate the recommended phase 2 dose (RP2D) of tarlatamab in combination with AMG 404 using a modified toxicity probability interval (mTPI-2) design. A combination RP2D may be identified based on emerging safety, efficacy, and pharmacodynamic data prior to reaching an MTD.

[figure not shown]

Table 4-1. Planned Target Doses per Dose Cohort Level

Dose Cohort Levels	Dose (mg) IV
-1	
1	
2	
3	

IV = intravenous

[figure not shown]
Footnotes are referenced from first-in-human study (Study 20160323)

To mitigate the risk of CRS and to potentially optimize the PD activity of tarlatamab, a step dosing approach with 1-step dosing will be implemented as part of the dosing schedule. Based on emerging safety data and the recommendations of the DLRM, the dosing schedule may be adjusted to allow for AMG 404 to be administered initially on

Protocol Number: 20200439

Date: 05 June 2024 Page 42 of 176

Part 1 may include one or more of the following planned dose levels of tarlatamab in combination with a fixed dose of AMG 404 (design in Figure 4-1):

[figure not shown]
- Dose Cohort Level 1: tarlatamab at a target dose of (with 1-step dosing) in combination with AMG 404 at beginning on cycle 1
- Dose Cohort Level 2: tarlatamab at a target dose of (with 1-step dosing) in combination with AMG 404 at mg IV beginning on cycle 1
- Dose Cohort Level 3: tarlatamab at a target dose of mg administered IV
 (with 1-step dosing) in combination with AMG 404 at mg IV
 beginning on cycle 1
- Dose Cohort Level -1: tarlatamab at a target dose of mg administered IV (with 1-step dosing) in combination with AMG 404 at mg IV (ir case Dose Cohort Level 1 is not well tolerated) beginning on cycle 1
- Dose Cohort Level -2: tarlatamab at a target dose of mg administered IV
 (with 1-step dosing) in combination with AMG 404 at mg IV (ir case Dose Cohort Level -1 is not well tolerated) beginning on cycle 1

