8.1.5 End of Study

The End of Study visit is defined as the date of the final study visit (eg, final long-term follow-up visit) when assessments and/or procedures are performed.

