8.4.7 Vital Status

Vital status must be obtained for all subjects within the limits of local law. This includes subjects who may have discontinued study visits with or without withdrawing consent and should include interrogation of public databases, if necessary. If deceased, the date and reported cause of death should be obtained.

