9.4.1 Planned Analyses

9.4.1.1 Interim Analysis and Early Stopping Guidelines

Safety data will be reviewed on an ongoing basis.

During dose exploration (Part 1) and formally during DLRMs, Amgen, in consultation with the site investigators, will review all available cumulative data by cohort prior to making dose escalation or dose de-escalation recommendation. Adverse events and DLTs observed in all subjects will be evaluated continually and fully integrated into all DLRMs and considered in all enrolment and dosing decisions.

Protocol Number: 20200439

Date: 05 June 2024 Page 108 of 176

During dose expansion (Part 2), Amgen will conduct evaluations of the ongoing grade 4 or higher treatment-related **treatment emergent adverse events** to assess if the threshold for possible early trial termination has been reached. The safety interim will occur for every subjects enrolled who have had opportunity to have at least days of follow up since the first dose of tarlatamab. If this threshold is met, enrollment to dose expansion will be halted pending review of safety data by the DLRT. After receiving the DLRT recommendation, Amgen will choose to take one of the following actions.

- 1) Terminate the trial
- 2) Amend the protocol to potentially improve the benefit/risk for subjects (eg, increase safety monitoring, modify dose/schedule, mandate premedication)
- 3) Continue dose expansion without any changes.

The stopping rules use a Bayesian approach proposed by Thall (Thall et al, 1995) to terminate the study if the posterior probability that the grade 4 or higher treatment-related **treatment emergent adverse event** rate is greater than 20% is > 80%. The stopping boundaries assume a prior distribution of Beta (0.40, 1.60) are presented in Table 9-2 and the operating characteristics with pre-specified batch size of new subjects per batch are presented in Table 9-3.

Table 9-2. Stopping Boundary for Dose Expansion with Posterior Probability of 80% and Grade 4 or Higher Treatment-related Adverse Event Limit of 20%

Number of Subjects	Stop Subjects if Observing This Many Grade 4 or Higher Treatment-related Adverse Events	
	≥ 4	
	≥ 6	
	≥ 9	
	Dose Expansion Complete	

Table 9-3 Operating Characteristics with Batch Size of Subjects

True Grade 4 or Higher Treatment-related Adverse Event Rate	Probability of Early Stopping of Dose Expansion	Average Dose Expansion Sample Size
0.10	2.0%	39.5
0.15	9.7%	37.6
0.20	25.8%	33.9
0.25	47.7%	28.8

Protocol Number: 20200439

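### Overall survival after month 12 is not reliably estimated: scheduled survival contact stops at 12 months, and the SAP sets no common vital-status date

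*Protocol*

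**What the plan says.** **Contact.** Protocol Section 8.1.4 has survival contact every 3 months, "up to 1 year from the first dose of tarlatamab for all subjects who have not withdrawn consent". Section 8.1.5 gives the final long-term follow-up visit as an example of the End of Study visit. In the Schedule of Activities (Tables 1-2, 11-8 and 11-9), survival status is marked only in the long-term follow-up column.

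**Treatment.** Protocol Section 1.2 says "treatment continues until confirmed radiographic progression or disease progression", and Section 7.2 allows it beyond progression with approval. There is no maximum duration.

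**Censoring.** SAP Section 5 censors a living subject for overall survival (OS) at the last-known-alive date. It builds that date from dosing, laboratory, vital-sign, ECG, imaging and survival-status forms, among others. The data cut-off pulls later dates back; it does not bring earlier ones forward.

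**Outputs.** SAP Table 7 and Section 9.5.2 plan the Kaplan-Meier (KM) curve, median and quartiles, with 6-month and 1-year rates as example landmarks.

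**Vital-status duty.** Protocol Section 8.4.7: "Vital status must be obtained for all subjects within the limits of local law". The duty reaches people who no longer attend visits, whether or not they have withdrawn consent, and public databases are to be searched if necessary. It gives no time point and asks for a date only when the subject has died. Section 7.3 adds that "where permitted, publicly available data can be included after withdrawal of consent".

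**The concern.** Up to month 12 every subject is under survival contact. After that, a subject on treatment is dated as alive at each visit, whereas a subject off treatment has no scheduled contact once safety follow-up is over. Who stays in the risk set then depends on treatment status, and treatment status is probably related to the risk of death, because treatment normally stops at confirmed progression. KM assumes that censored subjects have the same later risk as those who remain. If that fails, the late curve describes the wrong people.

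The period is not hypothetical. Protocol Section 4.1 says "Study enrollment ended in January 2023", and the SAP is dated 27 September 2024, about 20 months later. A late plateau resting on a few mostly on-treatment subjects could be read as durable benefit. A late fall produced by adding deaths alone could mislead the other way.

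**Working it through.** Neither document states a survival assumption, an event count or a precision for OS, so there is no figure of the plan's to reproduce. The steps below show the mechanism and an illustrative size. All rates are assumptions.

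**1. Who is observed after month 12.** Adverse events are collected for at least 60 days after the last dose (Protocol 8.4.9.1.1), so a subject who stops at month s is seen to about s + 2. With scheduled contacts alone, the risk set after month 12 is the subjects on treatment plus those who stopped within the last w = 2 months.

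**2. Assumed base case.** Rates per month:
- stopping treatment alive (median 4 months): μ = ln 2/4 = 0.1733
- death after stopping (median 9 months): h_off = ln 2/9 = 0.0770
- death on treatment, one quarter of that: h_on = 0.0193
- last scheduled contact exactly at month 12

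**3. True survival.** With k = μ + h_on = 0.1925 and c = μ/(k − h_off) = 0.1733/0.1155 = 1.5:

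S(t) = e^(−kt) + c[e^(−h_off·t) − e^(−kt)]

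- S(12) = 0.0992 + 1.5(0.3969 − 0.0992) = 0.546
- S(18) = 0.0313 + 1.5(0.2500 − 0.0313) = 0.359
- S(24) = 0.0098 + 1.5(0.1575 − 0.0098) = 0.231

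**4. KM from scheduled contacts alone.** In the risk set, the ratio of recently stopped to on-treatment subjects is b = c[e^((k − h_off)w) − 1] = 1.5(e^0.231 − 1) = 0.390. The observed hazard is λ = (h_on + b·h_off)/(1 + b) = (0.0193 + 0.0300)/1.390 = 0.0355. Then KM(t) = S(12)·e^(−λ(t − 12)):
- month 18: 0.546 × e^(−0.213) = 0.441, error +8.2 points
- month 24: 0.546 × e^(−0.425) = 0.357, error +12.5 points
- median: 12 + ln(0.5457/0.5)/0.0355 = 14.5 months, true 13.3
- time when 25% remain alive: 12 + ln(0.5457/0.25)/0.0355 = 34.0 months, true 23.0

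A simulation of 400,000 subjects, with last contact spread over months 11.5 to 12.5, agrees: 43.9% at 18 months and 35.7% at 24.

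**5. How the 18-month error moves.** Differences are from unrounded values.

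| Change from base case | True % | KM % | Error, points |
|---|---|---|---|
| None | 35.9 | 44.1 | +8.2 |
| On/off death-hazard ratio 0.5 (c = 1.286, b = 0.398, λ = 0.0495) | 31.5 | 36.2 | +4.7 |
| Equal hazards (λ = h_off) | 25.0 | 25.0 | 0 |
| Post-treatment contact 1 month (b = 0.184, λ = 0.0282) | 35.9 | 46.1 | +10.1 |
| Post-treatment contact 5 months (b = 1.173, λ = 0.0504) | 35.9 | 40.3 | +4.4 |
| 25% of later deaths found, alive dates not refreshed* | 35.9 | 35.6 | −0.3 |
| 50% found* | 36.0 | 33.1 | −2.9 |
| 100% found* | 35.9 | 30.9 | −5.0 |
| Everyone updated to one date* | 35.9 | 35.9 | 0 |

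*Simulated, cut-off at 30 months. At 24 months the three deaths-only rows give −4, −8 and −10 points.

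**6. Outputs touched.** The 6-month rate has no error. The 1-year rate has none if the last contact is at month 12, and about +0.1 to +0.5 points if it falls up to two weeks earlier. If contacts were counted so that the last fell anywhere in months 9 to 12, the assumed models give +0.9 to +3.1. With short survival (medians of 2 months on treatment and 4 after), the median (5.2 to 7.1 months) and upper quartile (9.6 to 11.6) fall before month 12 and do not change.

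**7. Against sampling error.** Cohort sizes are blacked out. I assume n = 40, because the column "Average Dose Expansion Sample Size" in Protocol Table 9-3 shows 39.5 at 2.0% early stopping. Expected numbers at risk at month 18 are 40 × 0.0313 × 1.390 = 1.7 with scheduled contacts alone, and 40 × 0.359 = 14.4 with a common date. The standard error with a common date is √(0.359 × 0.641/40) = 7.6 points, so the base-case error is about one standard error.

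**The case against.** The strongest defence is Protocol 8.4.7. It makes vital status mandatory for all subjects, including those who stopped visits, and Section 7.4 adds a public-records search for subjects lost to follow-up. If that is carried out for everyone at one date, nothing is wrong, and censoring at the last-known-alive date is ordinary practice. This stands in part. The duty exists, but it has no time point, the schedule places survival status only at long-term follow-up, and the SAP never turns the duty into a date.

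A reader might infer that the late OS curve is biased upward. The documents do not support that as a general statement. It needs two conditions: scheduled contacts are the only source, and the death hazard is lower on treatment than off it. The documents give no figure for the second. Section 8.4.7 also works against the first, and because it asks for a date only for deaths, partial compliance could reverse the sign. A reader might also infer that survival is not followed at all after month 12; Section 8.4.7 contradicts that.

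Other points that stand: 18-month OS is not a named landmark; the safety follow-up day counts are blacked out, so post-treatment contact may exceed two months; and the primary analysis, due once each subject has 6 months on study or has withdrawn, has less follow-up beyond month 12.

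**Conclusion.** OS after month 12 is not reliably estimated under the plan as written, because censoring there can depend on treatment status. The error is upward with scheduled contacts alone and a lower on-treatment hazard, downward if deaths are added without matching alive dates, and absent if every status is brought to one date. In the single-change variants of the base case, the 18-month error ran from about −5 to +10 points. It depends on the assumed hazard ratio, the length of post-treatment contact and the cut-off, so it is illustrative only.

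The exposed outputs are the curve after month 12, the upper quartile, and the median if it exceeds 12 months. OS is descriptive and no hypothesis is tested, so this is minor.

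**What to change.** Change SAP Section 5 (Overall Survival, Last Known Alive Date) and Section 9.5.2:

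- Before each analysis that reports OS beyond month 12, obtain vital status under Protocol 8.4.7 for every subject as of one data cut-off date. Record dated alive status as well as deaths, and use both for OS censoring. Report how many statuses could not be established.
- If this is not done, censor OS at 12 months from first dose, report later medians or quartiles as not estimable, and list later on-treatment follow-up separately.
- In both cases, print numbers at risk under the curve.

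The cost is SAP wording and one round of status checks by telephone, chart or public record, within local law. Because 8.4.7 already imposes the duty, no protocol amendment appears necessary. The downside is that subjects past month 12 may have completed their scheduled visits, so some statuses may not be obtainable. The fallback needs no new data but leaves late on-treatment follow-up out of the curve.
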